8. TREATMENTS

8.1 Treatments to be Administered

Sevoflurane group:

Anesthesia will be maintained with sevoflurane (gaseous form via the endotracheal tube) in 80% oxygen, adjusted to keep an adequate depth of anesthesia (minimal alveolar concentration (MAC) between 0.8 and 1.2, corresponding to an age adjusted sevoflurane expiratory concentration ranging from 1.5% to 2.5%), attested by BIS index values between 40 and 60. Drug administration will be limited to the length of the surgical procedure.

Propofol group:

Anesthesia will be maintained with a TCI device providing an intravenous propofol dose adjusted to keep an adequate depth of anesthesia (TCI values: start after induction with 2.0mcg/ml, then ranging from 3.0mcg/ml to 5.0 mcg/ml), attested by BIS index values between 40 and 60. Patients will be ventilated with 80% oxygen in air. Drug administration will be limited to the length of the surgical procedure.

Identity of Investigational Product(s)

Sevoflurane (test group)

Sevorane®, AbbVie, 250ml bottle

Propofol (control group)

Propofol-®Lipuro 1% (10mg/ml), B.Braun, 50ml glass bottle

8.2 Method of Assigning Subjects to Treatment Groups

Fixed randomization based on a 1:1 allocation ratio will be performed. Balanced treatment allocation will be ensured using block sizes of 4. Patients will be stratified according to their ASA class during the randomization process, which will be performed using a web-based interactive allocation platform (www.randomizer.at).

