7.1 Inclusion Criteria

- 18 to 85 years old
- Female patients
- Primary breast cancer without known remote extension
- Scheduled for tumor resection or mastectomy, +/- axillary node dissection
- ASA status I-III, as defined by the American Society of Anesthesiologists
- Capable of giving informed consent

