7.3 Subject Recruitment and Screening

All consecutive patients admitted for breast cancer surgery will be assessed for study eligibility by the anesthesiology staff. The attending anesthetist will inform patients about the study orally and in writing. Patients willing to participate will subsequently provide written informed consent. A pregnancy test will be performed.

Participation is on a strictly voluntary base. No compensation in any form will be granted to the subjects.

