8.6 Blinding

Adequate double-blinding will be performed: patients will not be told about their group assignments, the surgical team and nurses on the ward will not be informed during

the perioperative period about the anesthesia regimen provided, anesthesia records will be placed in sealed opaque envelopes at discharge from PACU and kept in a secure locker in the anesthesia office until the patient is discharged from the hospital. The pathologist responsible for histopathological assessment, the lab staff performing the CTC detection and the research fellow in charge for isolation and culture of NK cells (outcome assessors) will not have any access to the operation theatre or to the patient chart. The attending anesthesiologist responsible for randomization and providing the anesthesia and collecting the first two blood samples cannot *per se* be blinded but will not participate in any data collection or analysis. The study research team collecting the data will not have access to patient allocation until the final analysis.

In situations requiring a breach in the blinding process, such as the occurrence of SAEs, an Emergency Code Break will be available to the investigator. This Code Break should be opened only in emergency situations when the identity of the investigational product must be known by the investigator in order to provide appropriate medical treatment.

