12. STATISTICS

12.1 Statistical and Analytical Plans

This is a multicentric randomized controlled trial comparing the effect of 2 different anesthetic regimens (sevoflurane *versus* propofol) on perioperative levels of CTC in patients undergoing surgery for primary breast cancer.

Using a strict 4 time-points schedule, the number of CTC in peripheral blood will be measured before and after exposition to general anesthesia (primary outcome).

Using a mixed model analysis, the effect of two independent variables on the mean level of CTC will be explored: a within-subject time factor (i.e. variation of CTC levels over time) and a between-subject treatment factor (i.e. anesthesia regimen).

Fixed randomization based on a 1:1 allocation ratio will be performed using minimization (www.randomizer.at). Patients will be stratified according to their ASA class during the randomization process, which will be performed using a web-based interactive allocation platform (www.randomizer.at).

Accordingly, the risk of allocation and selection bias will be negligible. Restriction and stratified randomization are likely to minimize the risk of unbalanced known and unknown confounders. Blinding of participants and outcome assessors (laboratory staff, pathologist) will prevent measurement/detection bias.

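### A disclosed fixed block of 4, contradicted by minimization in Section 12.1, makes up to one third of allocations deducible if staff track them, so calling selection bias negligible is too strong

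*Protocol*

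**What the plan says.** Section 8.2 sets the allocation: "Fixed randomization based on a 1:1 allocation ratio will be performed", and "Balanced treatment allocation will be ensured using block sizes of 4". No other block size is named. On strata: "Patients will be stratified according to their ASA class during the randomization process". Center is not named as a factor. Section 7.1 admits "ASA status I-III, as defined by the American Society of Anesthesiologists", so there are at most three ASA strata.

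Section 12.1 describes the method differently: "Fixed randomization based on a 1:1 allocation ratio will be performed using minimization (www.randomizer.at". The same section then rates the risk of allocation and selection bias as negligible.

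On roles, Section 7.3 says "All consecutive patients admitted for breast cancer surgery will be assessed for study eligibility by the anesthesiology staff" and "The attending anesthetist will inform patients about the study orally and in writing". Section 6.1 places the eligibility check and consent on the day before surgery, and the randomization at the point where the patient is set up for induction; it rests concealment on that timing. Section 8.6 says "The attending anesthesiologist responsible for randomization and providing the anesthesia and collecting the first two blood samples cannot" be blinded. It also says that anesthesia records are sealed when the patient leaves the recovery unit and are locked away until hospital discharge.

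**The concern.** Concealment has two parts. The current assignment must be hidden until the patient is committed, and it must not be inferable from earlier assignments. Randomizing through a web platform at induction secures the first part. It does nothing for the second when the block size is fixed, small and printed in a document that the enrolling staff use.

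Here the group that decides whom to assess and inform is also the group that gives the study drug unblinded. A staff member who had followed the stratum could form an expectation about the next arm at the pre-operative visit, before the patient is asked. Inviting or deferring patients on that expectation would make the arms differ in prognosis at entry, which blinded laboratory assessment cannot undo. The protocol offers its assurance of negligible risk without addressing this route.

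The contradiction between Sections 8.2 and 12.1 adds to this. Permuted blocks and minimization are different procedures with different predictability, so the protocol does not establish which one the assurance describes.

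**Working it through.** The protocol gives no predictability figure, so there is none to reproduce.

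**Inputs.** Block size 4 and 1:1 ratio (Section 8.2); at most three ASA strata (Sections 7.1 and 8.2); 232 patients (Section 12.5); expected monthly enrollment of 5-10 at the university hospital and 3-8 at the second hospital (Section 7).

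**Full knowledge of the stratum list, block of 4.** There are six equally likely balanced sequences. The best guess is the arm with more places left in the block.

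| Place in block | Chance it is certain | Chance the best guess is right |
|---|---|---|
| 1 | 0 | 1/2 |
| 2 | 0 | 2/3 |
| 3 | 1/3 | 1/3 × 1 + 2/3 × 1/2 = 2/3 |
| 4 | 1 | 1 |

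- Certain share: (0 + 0 + 1/3 + 1)/4 = 1/3, or 232/3 ≈ 77 patients.
- Correct guesses: (1/2 + 2/3 + 2/3 + 1)/4 = 17/24 = 70.8%, against 50% by chance.
- A larger fixed block helps only moderately: size 6 gives 25.0% certain and 68.3% correct; size 8 gives 20.0% and 66.6%.

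**Partial knowledge.** Suppose an observer sees a random share q of the list and knows the position in the block. Place 3 is certain if both earlier draws were seen and are alike: q² × 1/3. Place 4 is certain if both like draws among the first three were seen: q². The certain share is therefore (q²/3 + q²)/4 = q²/3.

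- Midpoint enrollment is 7.5 and 5.5 per month, so the site shares are 7.5/13 = 0.58 and 5.5/13 = 0.42.
- If the hospitals share a list and staff pool everything seen at their own site: 0.58²/3 = 11% and 0.42²/3 = 6% certain.
- At q = 0.5, 8% are certain and simulation gives about 60% correct guesses. At q = 0.2, the figures are about 1% and 54%.

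**Randomly varying sizes (simulation, full history known and the set of sizes known).**

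| Sizes | Certain | Best guess right |
|---|---|---|
| 4 only | 33% | 71% |
| 4 and 6 | about 5.5% (about 13 of 232) | about 69% |
| 4, 6 and 8 | about 2% (about 5 of 232) | about 68% |

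**If Section 12.1 governs.** Deterministic minimization on ASA class alone forces every second draw: 50% certain and (1/2 + 1)/2 = 75% correct. With an assumed probability of 0.8 for the favored arm, simulation gives 0% certain and about 69% correct.

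**The case against.** The strongest reply is that the mechanism needs knowledge which the protocol does not say anyone has. Section 8.6 shows only that each attending anesthesiologist knows the patients he or she treats. Records are sealed after the recovery unit, and the data-collecting team has no access to allocations until the final analysis. Nothing says that the same individuals take consent and treat from case to case, or that anyone keeps a tally. Another patient randomized in the same stratum between consent and induction also weakens a prediction. This stands, and it is why one third and 70.8% are ceilings.

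There are further safeguards. Consecutive patients are assessed (Section 7.3) and those not enrolled go on a screening log (Section 13), so selective invitation would leave a trace. Circulating tumor cells are measured before induction (Section 6.2) and the laboratory staff are blinded. These limit the damage and help detect it, but they do not prevent selection on prognosis that is not measured.

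A reader might infer that the enrolling staff do see past allocations and will predict many upcoming ones, or that any resulting bias would be beyond repair. The documents support neither. Overlap of staff group is documented; shared knowledge of the list is not. A baseline measurement of the outcome itself is available for adjustment.

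The shared list is also an inference, drawn from ASA class being the only named factor. If each hospital has its own list, local staff could in principle see all of it, and the truth could lie nearer the ceiling than the 6-11% range.

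**Conclusion.** The point holds as a conditional weakness that should be corrected. Section 8.2 fixes and discloses a block size that allows up to one third of allocations to be deduced and up to 70.8% to be guessed, given complete tracking of a stratum. With single-site knowledge of a shared list, about 6% to 11% are certain, assuming that staff pool what they see and know their place in the block.

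The protocol does not justify calling the risk negligible, because its stated safeguard covers only the current draw. The documents give no evidence that prediction or selective enrollment occurs.

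The conflict between blocks in Section 8.2 and minimization in Section 12.1 is an error on the face of the protocol. It must be settled first, since the block figures apply only if Section 8.2 governs. Minimization would not by itself remove the problem: on ASA class alone and without a random element, it would be more predictable than blocks of 4.

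**What to change.** 1. State one allocation method and make Sections 8.2 and 12.1 agree.
2. If permuted blocks are used, set the web platform to randomly varying sizes within strata, for example 4, 6 and 8. Delete the block size from the protocol and keep it in a randomization document with restricted access.
3. If minimization is used, state that it includes a random element, and keep the probability in the same restricted document.
4. Soften the claim in Section 12.1: allocation is concealed until induction and predictability is limited by the chosen method.
5. Optionally, where staffing allows, have consent taken by someone who does not treat trial patients. This addresses the mechanism directly, which matters because varying the sizes leaves the best-guess rate at about 68%.

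Items 1 to 4 cost a platform setting and a few sentences in an amendment. The statistical price is small. The maximum mid-block imbalance per stratum rises from 2 to 4 patients, so the worst case over three strata rises from 6 to 12 (122 against 110 of 232). Even then, relative efficiency for a simple two-group comparison is (122 × 110)/116² = 13,420/13,456 = 99.7%. Item 5 costs staff time.

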7. SUBJECT SELECTION AND WITHDRAWAL

Patients undergoing surgery for breast cancer will be enrolled at the University Hospital of Zürich (USZ) and at Klinik Hirslanden Zurich. The Department of Gynecology and Breast Cancer Center of the USZ perform about 150-200 operations per year for breast cancer. Based on USZ last year records, we expect to enroll 5-10 patients per month; slightly lower enrollment rates are expected at Klinik Hirslanden, (3-8 patients/month).

Meetings with the anesthesia team USZ and the investigators of Klinik Hirslanden will be organized periodical at least all 6 month, to identify at an early stage potential enrolment or organizational issues. These meetings are also expected to act as a positive feedback and motivational tool.

Patients fulfilling all of the following inclusion criteria will be enrolled in the study:

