8.3.2 Medications susceptible to interfere with outcome measure

8.3.2.1 Opioids

Since opioids have been suggested to inhibit the immune function,⁸⁴ per- and postoperative analgesia will be provided following a **standardized protocol**:

- Fentanyl 2mcg/kg (total dose ranging from 5-10mcg/kg) will be used during surgery
- Surgical wound infiltration with local anesthetics will not be allowed
- Morphine intravenous 0.02-0.04mg/kg for a VAS <4 will be used in the PACU
- Basic postoperative analgesia will be provided using paracetamol and non-steroidal anti-inflammatory drugs
- Subcutaneous morphine 0.1-0.2mg/kg will be prescribed as second line analgesic on the ward (reserve medication)

With the aim to obtain high protocol compliance, postoperative analgesics in USZ will be prescribed in the patient electronic chart (KISIM) following a predefined schema saved in the KISIM database. The attending anesthesiologist has access to the database and will upload this schema to the electronic patient chart, regardless of the assignment group.

For patients enrolled at Klinik Hirslanden, postoperative analgesics will be prescribed using a standardized paper form specifically designed for this study.

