12.3.1 Primary Analyses

The primary endpoint, i.e. blood CTC levels, is a continuous variable. In our study, 2 independent variables may interact with CTC levels: a time factor, which results from repeated measurements over time (i.e. within-subjects factor) and an intervention factor, which is the anesthesia regimen (between subjects factor). Thus, our primary analysis will be performed using a linear mixed model with random effects matrix to account for within-subjects correlated observations as indicated for longitudinal data analysis.

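### The primary mixed model names only time and regimen, leaving out ASA class (a randomisation stratum) and centre (two hospitals recruit); this costs some precision but causes no bias

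*Protocol*

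**What the plan says.** **Centres.** Section 12.1 opens: "This is a multicentric randomized controlled trial comparing the effect of 2 different anesthetic regimens". Section 7 names the two sites: "Patients undergoing surgery for breast cancer will be enrolled at the University Hospital of Zürich (USZ) and at Klinik Hirslanden Zurich". For the university hospital, "we expect to enroll 5-10 patients per month"; for the other site, "slightly lower enrollment rates are expected at Klinik Hirslanden, (3-8 patients/month" is the expectation.

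**Allocation.** Section 8.2: "Patients will be stratified according to their ASA class during the randomization process", and "Balanced treatment allocation will be ensured using block sizes of 4". Section 12.1 also names ASA class as the only factor but describes the method as minimization. Centre appears in neither section.

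**Primary model.** Section 12.3.1: "In our study, 2 independent variables may interact with CTC levels". The two are time (within subject) and regimen (between subjects), as in section 12.1. Random effects handle the repeated measurements.

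**Adjustment.** Section 12.3.2 allows further exploratory analyses if residual confounding calls for them, and section 8.4 promises analytical adjustment for residual confounders. ASA class is collected (Table 4). Centre is not on the list of potential confounders in section 5.2.3 or in Table 4, although it is known for every patient.

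**The concern.** A factor used to restrict randomisation normally belongs in the analysis. If it predicts the outcome, the allocation has made the arms more alike than simple randomisation would, and a model without the factor does not credit that. Here ASA governs allocation but is missing from the named model.

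Centre is in a different position. It is not balanced by design and not in the model, so the arms can differ by chance in their mix of hospitals, and any centre difference in CTC counts stays in the residual noise. The only route to adjustment is conditional and exploratory, so covariates could be chosen after the imbalance has been seen.

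What is at stake is efficiency. The trial is sized for 80% power at an effect of 0.3, with no visible slack.

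**Working it through.** **1. The plan's own sample size.** Inputs from section 12.5: effect 0.3, within-subject correlation 0.4, two-sided 5%, 80% power, 10% dropout. The number of measurements is not stated; three post-exposure samples reproduce the figure.

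- One measurement: 2 × ((1.960 + 0.842)/0.3)² = 174.4 per arm.
- Mean of three: factor (1 + 2 × 0.4)/3 = 0.60, so 174.4 × 0.60 = 104.65.
- Dropout: 104.65/0.9 = 116.3, against the stated 116.

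The figure is not in dispute. It shows that the baseline scale is a variance of 0.60 SD² for the three-visit mean, with about 104 analysed per arm (116 × 0.9).

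**2. Chance imbalance in centre.** Second-site share from section 7:

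- low with low, 3/(3 + 5) = 37.5%; high with high, 8/(8 + 10) = 44.4%;
- crossed extremes, 3/(3 + 10) = 23% and 8/(8 + 5) = 62%. The upper extreme sits badly with the statement that the second site recruits slightly less, but it is kept as a bound.

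With K second-site patients among 232 and x of them in one arm of 116, x is hypergeometric and the gap in centre share is |2x − K|/116. The chance that the gap is 10 points or more:

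| K (share) | Chance |
|---|---|
| 87 (37.5%) | 10.3% |
| 103 (44.4%) | 11.3% |
| 54 to 143 (23–62%) | 6.3% to 14.8% |

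The gap moves in steps of 2/116, so odd and even K differ by a few points; even K between 87 and 103 gives about 14–15%.

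A simulation of blocks of 4 stratified by ASA alone (assumed ASA I/II/III mix 25/60/15%) agrees: a gap above 10 points in 7–13% of trials, with a standard deviation of about 6.5 points at a 42% share. With ASA × centre strata the standard deviation is about 1 point, and no simulated trial exceeded 10.

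**3. Precision.** Let ASA and centre together explain a share f of total variance, with an effect that is constant over time. The protocol gives no value for f; 1%, 5% and 10% are assumptions. After adjustment the variance at one visit is 1 − f and the covariance between visits is 0.4 − f. The variance per patient of the treatment contrast is then:

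- post-exposure mean, baseline unused: 0.60 − f;
- baseline-adjusted: (0.60 − f) − (0.40 − f)²/(1 − f);
- change from baseline: (0.60 − f) + (1 − f) − 2(0.40 − f) = 0.80 for any f.

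| f | Post mean | Cut | Baseline-adjusted | Cut | Change | Cut |
|---|---|---|---|---|---|---|
| 0 | 0.60 | – | 0.440 | – | 0.80 | – |
| 1% | 0.59 | 1.7% | 0.436 | 0.8% | 0.80 | 0 |
| 5% | 0.55 | 8.3% | 0.421 | 4.3% | 0.80 | 0 |
| 10% | 0.50 | 16.7% | 0.400 | 9.1% | 0.80 | 0 |

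For the post-exposure mean only, with 104 per arm, adjusted power is 80.4%, 83.1% and 86.4%, against 79.8% at f = 0.

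**4. Omitting a balanced factor.** If the whole of f belongs to ASA, the model assumes 0.60 while the true variance is 0.60 − f. The critical value is in effect 1.960 × √(0.60/(0.60 − f)). True type I error is 0.048, 0.041 and 0.032, and power is 80.0%, 80.8% and 81.9%. The test is conservative, not anti-conservative. This too is for the post-exposure mean; for a pure change contrast there is nothing to lose.

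**The case against.** **Covariates belong to the SAP, which is not shown.** This is partly right. An SAP may add ASA and centre. But the protocol is not merely silent: it counts the independent variables as two and describes covariate adjustment only as a remedy for residual confounding. A later document would have to extend what the protocol fixes.

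**Nothing is invalid.** This stands in full. A reader might infer that unbalanced centres bias the comparison. They do not: 1:1 randomisation is unbiased without centre strata, and chance imbalance is already within the test's error rate.

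**The gain may be small or nil.** This also stands. A reader might take the 8–17% cut for f = 5–10% as the expected benefit, but it needs a contrast that ignores the pre-induction sample, whereas the plan models four time points including that sample. No passage says that ASA or centre predicts CTC counts, so values of f near zero are possible.

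**The sites are harmonised.** This stands. A reader might infer that opioid use or surgery differs by hospital. Sections 8.3.2.1 and 8.3.2.2 describe one standardised scheme in which only the prescribing medium differs: "For patients enrolled at Klinik Hirslanden, postoperative analgesics will be prescribed using a standardized paper form specifically designed for this study". Section 9.1 sends CTC samples to one laboratory within 96 hours without singling out a site, and no surgical difference is described. Nor does the protocol show that the second hospital joined late.

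**Conclusion.** The point holds as an efficiency matter. The primary model leaves out a factor that governs allocation and the hospital at which the patient is treated, and both are known for every patient. Centre imbalance of 10 points or more has roughly a 6–15% chance, which follows from the stated accrual and sample size. The loss of precision ranges from nothing to about 17% of the variance, depending on which contrast the model tests and on an assumed 1–10% of variance explained; with baseline adjustment it is about 1–9%. The treatment estimate stays unbiased, and omitting ASA errs on the conservative side. The change is worth making because it costs almost nothing, not because the present plan would give a wrong answer.

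**What to change.** In section 12.3.1, state that ASA class and centre enter the primary linear mixed model as fixed effects, whatever the observed balance. Say the same for the NK models and the logistic mixed model in section 12.3.2, noting that the odds ratio there becomes conditional on both factors. With two hospitals, a fixed centre effect is more suitable than a random one. Bring section 12.1 into line and add centre to Table 4.

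Cost: two degrees of freedom for three ASA classes and one for centre, with no new data collection.

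Optional, if recruitment is still open: add centre as an allocation factor. First reconcile section 8.2 (blocks of 4) with section 12.1 (minimization), since that decides how the factor would be applied. Under stratified blocks, three strata become six, with slightly more incomplete blocks. If the allocation can no longer change, the model terms suffice.
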